9.8 Quality Control

9.8.1 Ethics and Quality

Prior to any study-related data being collected, informed consent form will be reviewed, signed and dated by the patient and the person who administered the informed consent. A copy of the signed informed consent will be given to the patient and the original will be placed in the patient's medical record.

9.8.2 Quality Assurance

Prior to the initiation of the study, physician and site personnel will be trained on the study. Training will include a detailed discussion of the protocol, performance of study procedures, and completion of the CRFs and paper questionnaires.

All sites will be monitored during the course of study participation. One hundred percent (100%) source document review for safety will be performed.

All clinical data will be documented via the CRF. Study coordinators at each site will check the paper CRFs completed by the physicians and questionnaires completed by patients (e.g., all questions were answered). Data entry will be conducted by IMS. After entry of the data, computer logic checks will be run to check for inconsistent data. Any necessary corrections will be made to the database and documented via addenda, queries, and source data clarification forms.

Steps to be taken to ensure the accuracy and reliability of data include the selection of qualified investigators and appropriate study centers, review of protocol procedures with the investigator and associated personnel before the study and periodic monitoring visits by the sponsor. Written instructions will be provided for administration and collection of study questionnaires.

Guidelines for CRF completion will be provided and reviewed with study personnel before the start of the study. The sponsor will review CRFs and patient questionnaires for accuracy and completeness after transmission to the sponsor; any discrepancies will be resolved with the investigator or designee, as appropriate. After upload of the data into the clinical study database they will be verified for accuracy and consistency with the data sources.

Protocol Deviation

For the purposes of this protocol, reportable deviations are defined as:

- Subject entered into the study even though she/he did not satisfy entry criteria
- Subject who developed withdrawal criteria during the study and was not withdrawn
- Subject who received wrong treatment
- Subject who received excluded or prohibited concomitant treatment

9.9 Limitations of the Research Methods

The study is to be performed as a non-interventional study. Unlike clinical studies, obtainable data are limited and there is a possibility of missing data.

9.10 Other Aspects

9.10.1 Note To File

The Principal Investigator or designee will be responsible for documenting study relevant information and occurrences that affects the course of the study. The information and occurrences are not protocol deviations but will be documented in a note to file and will be communicated to the sponsor.

9.10.2 Training Log

All designated study personnel must be trained on the study protocol and procedures. Training and retraining are documented on the Training Log.

9.10.3 Visitor Log

All Sponsor or other related individuals who visit the study site must sign the Visitor Log.

9.10.4 Responsibilities of the Principal Investigator

The Principal Investigator is responsible for oversight of enrolment, the patient consent process, study related procedures, compliance with the protocol, all institutional, state and local guidelines.

It is the responsibility of the Principal Investigator to select, supervise, and delegate responsibility for study conduct to staff members. The Principal Investigator is

responsible for determining the appropriate staff qualifications required for specific study-related tasks to be delegated. Study-related tasks delegated to staff members will be documented on the Site Signature and Delegation Log.

9.10.5 End of Trial

End of Trial is defined as last subject's last visit (LPLV).

10.0 Protection of Human Subjects

This study must be conducted in compliance with the recommendations of the Declaration of Helsinki, 2008 (World Medical Association). In addition, this study will adhere to all general and local legal and regulatory requirements applicable to non-interventional studies.

Informed consent will be obtained from each subject before the subject can participate in the study. The contents and process of obtaining informed consent will be in accordance with all applicable regulatory requirements.

As required by applicable local regulations, the sponsor's Regulatory Affairs group will ensure all legal regulatory aspects are covered, and obtain approval of the appropriate regulatory bodies, prior to study initiation in regions where an approval is required.

This study is non-interventional and falls outside the scope of the EU Directive 2001/20/EC, the EU Directive 2005/28/EC and International Conference on Harmonization (ICH) Good Clinical Practice (GCP) guidelines.

This study complies with the EU Directive 95/46/EC of the European Parliament and of the Council of 24 October 1995 on the protection of individuals with regard to the processing of personal data and on the free movement of such data.

11.0 Management and Reporting of Adverse Events/Adverse Reactions

11.1 Adverse Event Definition and Serious Adverse Event Categories

An adverse event (AE) is defined as any untoward medical occurrence in a patient, which does not necessarily have a causal relationship with their treatment. An adverse event can therefore be any unfavorable and unintended sign (including an abnormal laboratory finding), symptom, or disease temporally associated with the use of a medicinal product, whether or not the event is considered causally related to the use of the product.

Such an event can result from use of the drug as stipulated in the labeling, as well as from accidental or intentional overdose, drug abuse, or drug withdrawal. Any worsening of a pre-existing condition or illness is considered an adverse event.

If an adverse event meets any of the following criteria, it is considered a serious adverse event (SAE):

Death of Patient:	An event that results in the death of a patient.
Life-Threatening:	An event that, in the opinion of the investigator, would have resulted in immediate fatality if medical intervention had not been taken. This does not include an event that would have been fatal if it had occurred in a more severe form.
Hospitalization:	An event that results in an admission to the hospital for any length of time. This does not include an emergency room visit or admission to an outpatient facility.
Prolongation of Hospitalization:	An event that occurs while the study patient is hospitalized and prolongs the patient's hospital stay.
Congenital Anomaly:	An anomaly detected at or after birth, or any anomaly that results in fetal loss.
Persistent or Significant Disability/Incapacity:	An event that results in a condition that substantially interferes with the activities of daily living of a study patient. Disability is not intended to include

experiences of relatively minor medical significance such as headache, nausea, vomiting, diarrhea, influenza, and accidental trauma (e.g., sprained ankle).

Important Medical Event Requiring Medical or Surgical Intervention to Prevent Serious Outcome:

An important medical event that may not be immediately life-threatening or result in death or hospitalization, but based on medical judgment may jeopardize the patient and may require medical or surgical intervention to prevent any of the outcomes listed above (i.e., death of patient, life threatening, hospitalization, prolongation of hospitalization, congenital anomaly, or persistent or significant disability/incapacity). Additionally, any elective or spontaneous abortion or stillbirth is considered an important medical event. Examples of such events include allergic bronchospasm requiring intensive treatment in an emergency room or at home, blood dyscrasias or convulsions that do not result in inpatient hospitalization, or the development of drug dependency or drug abuse.

11.2 Severity

The following definitions will be used to rate the severity for any adverse event being collected as an endpoint/data point in the study and for all serious adverse events.

- Mild:** The adverse event is transient and easily tolerated by the patient.
- Moderate:** The adverse event causes the patient discomfort and interrupts the patient's usual activities.
- Severe:** The adverse event causes considerable interference with the patient's usual activities and may be incapacitating or life threatening.

11.3 Relationship to Pharmaceutical Product

The following definitions will be used to assess the relationship of the adverse event to the use of product:

Reasonable Possibility	An adverse event where there is evidence to suggest a causal relationship between the product and the adverse event.
No Reasonable Possibility	An adverse event where there is no evidence to suggest a causal relationship between the product and the adverse event.

If no reasonable possibility of being related to product is given, an alternate etiology must be provided for the adverse event.

11.4 Serious Adverse Event Collection Period

Serious adverse events will be reported to AbbVie from the time the physician obtains the patient's authorization to use and disclose information (or the patient's informed consent) until 70 days following the intake of the last dose of adalimumab taken during the study.

11.5 Serious Adverse Event Reporting

In the event of a serious adverse event, the physician will:

- For events from patients using an AbbVie product - notify the AbbVie Emergency contact person (ASR) identified at the beginning of the protocol within 24 hours of the physician becoming aware of the event.

11.6 Pregnancy Reporting

Pregnancies in patients will be collected from the date of the first dose through 150 days following the last dose of adalimumab taken during the study. In the event of a pregnancy occurrence in the patient, the physician will notify AbbVie Emergency contact person identified in protocol section 3.0 within 24 hours of the physician becoming aware of the pregnancy.

Information regarding a pregnancy occurrence in a study subject and the outcome of the pregnancy will be collected.

This protocol requires all SAEs and AESIs as outlined in protocol section 11.1 to be actively solicited. The safety profile of adalimumab which has over 3.5 million patient years of post-marketing exposure is stable and well established; non-serious events will not be actively solicited as these events are not likely to contribute to the further

understanding of the safety profile of the product. Any non-serious AEs will be collected as spontaneous reports if AbbVie is notified.

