9.2.5 Adverse Events

Adverse events, whether in response to a query, observed by site personnel, or reported spontaneously by the subject will be recorded. Adverse events definition and serious adverse event categories are described in detail in Section 11.0.

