9.2.6 Removal of Subjects from Therapy or Assessment

1. Discontinuation of Individual Subjects

A subject may withdraw from the study at any time. The Investigator may discontinue any subject's participation for any reason, including an adverse event, safety concerns or failure to comply with the protocol.

Subjects will be withdrawn from the study immediately if any one of the following occurs:

- Clinically significant abnormal laboratory result(s) or adverse event(s), as determined by the Investigator in consultation with the AbbVie Medical Monitor.
- The Investigator believes it is in the best interest of the subject.
- The subject requests withdrawal from the study.
- Inclusion and exclusion criteria violation was noted after the subject started study drug, when continuation of the study drug would place the subject at risk as determined by the AbbVie Medical Monitor (see *Section 5.2 and Section 7.0*).

- Introduction of prohibited medications or dosages when continuation of the study drug would place the subject at risk as determined by the AbbVie Medical Monitor.
- Subject is non-compliant with TB prophylaxis.
- The subject becomes pregnant while on study medication.
- Subject has dysplasia of the gastrointestinal tract or a malignancy, except for localized non-melanoma skin cancer. Discontinuation for carcinoma in-situ of the cervix is at the discretion of the Investigator.
- Subject is diagnosed with lupus-like syndrome, multiple sclerosis or demyelinating disease.
- Subject is significantly non-compliant with study procedures which would put the subject at risk for continued participation in the trial, as determined by the Investigator, in consultation with the AbbVie Medical Monitor.

Following discontinuation of the study drug, the subject will be treated in accordance with the Investigator's best clinical judgment. A final phone call will be made to the subject approximately 70 days after the last dose of study drug to determine the status of any ongoing AEs/SAEs or the occurrence of any new AEs/SAEs.

For subjects that are considered lost to follow-up, reasonable attempts should be made to obtain information on the final status of the subject.

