9.4 Data Sources

Case Report Forms (CRFs) and patient questionnaires.

Collection of data includes but not limited to subject demographics, clinical history, comorbidities, spontaneous adverse events, and concomitant medications. The following questionnaires will be utilized to collect data directly from participating subjects:

- EQ-5D
- SF-36
- HAQ DI
- WPAI
- HCRU
- Patient Global Impression of Change (PGIC)
- Patient Treatment Satisfaction Questions

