9.7.8 Safety Analysis

Adverse events occurring while participants are on adalimumab will be coded using Common Terminology Criteria for Adverse Events (CTCAE) classification individually listed by indication groups. The incidences and percentages of individuals experiencing AEs and SAEs within each indication will be summarized by System Organ Class (SOC) with further summaries by severity and relatedness (causality) categories. Adverse events leading to discontinuation and concomitant medications will also be listed and summarized.

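### Non-serious adverse events have no single collection rule, yet Protocol 9.7.8 plans incidence percentages for all AEs, which may be understated and may mix two ascertainment methods

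*Protocol*

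**What the plan says.** Four parts of the protocol bear on how a non-serious adverse event reaches the database.

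- **Section 9.2.5:** "Adverse events, whether in response to a query, observed by site personnel, or reported spontaneously by the subject will be recorded". There is no limit to serious events. The adverse event row in Table 1 is likewise not restricted to serious events.
- **Section 9.2.6:** for subjects who stop the drug, a phone call about 70 days after the last dose is made "to determine the status of any ongoing AEs/SAEs or the occurrence of any new AEs/SAEs".
- **Section 11.6 (Pregnancy Reporting):** "This protocol requires all SAEs and AESIs as outlined in protocol section 11.1 to be actively solicited", whereas "non-serious events will not be actively solicited as these events are not likely to contribute" to further understanding of the safety profile. It adds: "Any non-serious AEs will be collected as spontaneous reports if AbbVie is notified".
- **Section 9.4:** the data collected include "subject demographics, clinical history, comorbidities, spontaneous adverse events, and concomitant medications". The Abstract and SAP 3.3.1 use the same description.

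The analysis is in section 9.7.8. It covers one period, "Adverse events occurring while participants are on adalimumab will be coded using" a standard classification, and plans that "The incidences and percentages of individuals experiencing AEs and SAEs within each indication will be summarized by System Organ Class (SOC". The same counts are then split by how severe the event was and by its causal relation to the drug. Section 9.7.2 includes every subject with at least one dose. SAP 5.2 to 5.5 and the table list in SAP 6 contain no adverse event analysis.

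**The concern.** A percentage of patients with an adverse event can be read as an incidence only if events were sought in the same way from everyone in the denominator. If non-serious events enter the numerator only when volunteered and passed to the sponsor, while every dosed patient is in the denominator, the result is a reporting proportion. Missed reports can only lower it.

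The protocol does not settle which situation applies. A coordinator working from 9.2.5 could ask about and record non-serious events. One working from 11.6 would not ask, and would depend on notification. The 11.6 rule sits under a heading where few would look for it, and the pointer from 9.2.4 to the adverse event procedures is a broken cross-reference. The planned table gives the reader no sign of which rule produced its counts. That matters for a study whose results are meant for payers and health authorities.

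**Working it through.** **Stated figure.** The documents give no adverse event rate and no reporting completeness, so there is nothing to reproduce. The check is mainly a comparison of texts.

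**Step 1: collection rules side by side.**

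| Source | Non-serious AEs |
|---|---|
| Protocol 9.2.5 | Recorded, including those found in response to a query |
| Protocol Table 1 | AE row not limited to serious events |
| Protocol 9.2.6 | Call asks about new AEs as well as SAEs |
| Protocol 11.6 | Not solicited; spontaneous reports only, if the sponsor is notified |
| Protocol 9.4, Abstract; SAP 3.3.1 | Only spontaneous AEs named, in a list introduced as non-exhaustive |

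The clearest conflicts with 11.6 are the reference to a query in 9.2.5 and the call in 9.2.6, since asking about new events is solicitation. The call shows the inconsistency in the collection rule. It adds less to the 9.7.8 table, which counts events while on adalimumab, whereas the call comes about 70 days after the last dose.

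**Step 2: which percentages are exposed.** SAEs are solicited under 11.6 and have their own collection period (11.4) and 24-hour reporting (11.5). Under-capture therefore applies only to patients whose events are all non-serious. Let s be the proportion with a serious event, n the proportion with non-serious events only, and c the probability that a patient in the second group is captured:

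- reported all-AE proportion = s + n × c
- true all-AE proportion = s + n
- shortfall = n × (1 − c), which is never negative
- SAE proportion = s, whatever c is

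**Step 3: illustration.** The values of s, n and c are assumptions; none comes from the documents. Take s = 5%, n = 20% and the protocol's 52 patients. The true figure is 5% + 20% = 25%, or 13 of 52.

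| c | Reported | Patients of 52 | Shortfall |
|---|---|---|---|
| 30% | 5% + 20% × 0.30 = 11% | about 6 | 14 points |
| 50% | 5% + 20% × 0.50 = 15% | about 8 | 10 points |
| 80% | 5% + 20% × 0.80 = 21% | about 11 | 4 points |

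With n between 10% and 40% and c between 30% and 80%, the shortfall runs from 10% × 0.20 = 2 points to 40% × 0.70 = 28 points.

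**Step 4: mixed rules.** If half the patients were at sites that query and half at sites with c = 50%, the halves would show 25% and 15%, and the pooled figure would be (25% + 15%)/2 = 20%. That number describes neither method. The SAE figure stays at 5% throughout.

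**Step 5: the AESI reference.** Section 11.6 relies on 11.1 for the AESIs to be solicited. Section 11.1 defines adverse events and the SAE categories and names no AESI, so that part of the rule has no content.

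**The case against.** The two rules can largely be read together. Section 9.2.5 governs what is recorded once an event comes to light and does not order sites to ask about non-serious events; 11.6 governs what is solicited. On that reading, queries concern serious events, and non-serious ones are recorded when observed or volunteered. The wording in 9.4, the Abstract and SAP 3.3.1 fits this. It stands to the extent that the rules are inconsistent rather than opposite. It does not account for the 70-day call, or for an event observed by site personnel, which must be recorded under 9.2.5 but depends on notification under 11.6.

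A reader might infer that the safety percentages will certainly be understated and will not be comparable between sites. The documents do not support that. No percentages are stated, only planned. If every site follows 11.6, collection is incomplete but uniform. Sites differ only if they apply different rules, and no between-site comparison is planned.

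It is also fair that safety is not a study objective or endpoint, that 11.6 openly gives its reason for limited collection, that 9.9 acknowledges limited and possibly missing data, and that SAEs, pregnancy and malignancy in patients aged 30 and younger have explicit reporting rules. These points limit the consequence. They do not tell the reader of a 9.7.8 table how its non-serious events were found.

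The AESI gap may be a stale cross-reference: section 7.0 sends the malignancy requirement to a subsection, 11.1.2b, that does not exist, while the same text in 11.7 points to 11.7. That makes it editorial, but it still needs correcting.

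**Conclusion.** The concern holds in limited form. Protocol 9.2.5, Table 1 and 9.2.6 are inconsistent with 11.6 and 9.4 on non-serious adverse events, and 9.7.8 plans incidence percentages without distinguishing solicited from spontaneous events. The all-AE and non-serious percentages, including their splits by severity and relatedness, may be understated and may mix two ascertainment methods. Any error from missed reports is downward. SAE percentages are unaffected, provided sites solicit SAEs as 11.6 requires.

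The size cannot be derived from the documents; the 4 to 14 point shortfall in the main illustration depends entirely on assumed values. It would be tempting to apply incomplete capture to the whole adverse event rate, or to conclude that the drug will look better tolerated than it is. The first ignores the solicitation of SAEs. The second goes beyond the documents, which give neither a rate nor a completeness figure, and the study has no comparator. What is lost is the right to read the all-AE percentage as an incidence.

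**What to change.** 1. Reconcile Protocol 9.2.5, 9.2.6, 9.4, 11.6 and Table 1 into one collection rule for non-serious adverse events. Place it in the adverse event section, refer to it from 11.6, and repair the broken pointer in 9.2.4. The sponsor should choose the rule; the need is that there be only one.
2. In 9.7.8, report incidence only for systematically collected events, meaning SAEs and any listed AESIs. If non-serious events stay unsolicited, summarise them separately, labelled as spontaneously reported and not interpreted as incidence. Counts and percentages can remain under that label.
3. List the AESIs in 11.1 or delete the reference in 11.6.
4. Carry the same labels into the SAP if a safety table is added there.

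If the unsolicited rule is kept, the cost is wording and table labels, with no extra data, and a safety table that looks less complete. Choosing solicitation would add work at sites and could not be applied to visits already past. The labelling can still be done after data collection has ended (planned for 30 June 2018), provided it reflects what sites actually did.

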11.7 Malignancy Reporting

In the event of a serious adverse event, and additionally, any non-serious event of malignancy in patients 30 years of age and younger, whether related to study drug or not, the physician will notify the AbbVie contact person identified in protocol section 3.0 within 24 hours of the physician becoming aware of the event.

Adalimumab therapy has a well-established and well described safety profile based on extensive postmarketing experience and continued clinical trial patient exposure since the first approved indication in 2002 for rheumatoid arthritis. A detailed discussion of the pre-clinical toxicology, metabolism, pharmacology and safety experience with adalimumab can be found in the current Investigator's Brochure. AbbVie is committed to continue to collect safety information including those events that may occur in this trial in order to confirm this established safety profile and to identify any unknown potential adverse reactions, rare events and those events with a long latency. AbbVie is participating in an FDA-requested, TNF inhibitor class wide exploration of the rare appearance of malignancy in subjects/patients who are 30 years of age or younger at the time of diagnosis. The risk of malignancy in this age group has not been established and is difficult to study due to its rarity. AbbVie appreciates your attention to the additional reporting requirements needed in this unlikely event, outlined in Section 11.7 under Malignancy Reporting.

